3. PATIENT SELECTION, ENROLMENT, RESTRICTIONS, DISCONTINUATION AND WITHDRAWAL

Each patient should meet all of the inclusion criteria and none of the exclusion criteria for this study. Under no circumstances can there be exceptions to this rule.

3.1 Inclusion criteria

For inclusion in the study patients should fulfil the following criteria:

1. Provision of informed consent prior to any study specific procedures.
2. Patients aged ≥ 18 . For patients aged < 20 years, a written informed consent should be obtained from the patient and his or her legally acceptable representative.
3. Two consecutive i-STAT potassium values, measured 60-minutes (± 15 minutes) apart, both ≥ 5.1 mmol/L and measured within 1 day before the first dose of ZS on Correction Phase Study Day 1.
4. Patients who are on peritoneal dialysis (PD) can be enrolled if their SK level is ≥ 5.5 and ≤ 6.5 mmol/L in two consecutive i-STAT potassium evaluation at least 24 hours apart before Day 1 (in each evaluation, two i-STAT potassium measurements at least 1 hour apart are required). i-STAT potassium measurement should be performed in the morning before breakfast and in the evening before dinner in PD patients on continuous ambulatory peritoneal dialysis (CAPD) and automated peritoneal dialysis (APD), respectively.
5. Ability to have repeated blood draws or effective venous catheterization.
6. Women of childbearing potential must be using 2 forms of medically acceptable contraception (at least 1 barrier method) and have a negative pregnancy test within 1 day prior to the first dose of ZS on Correction Phase Study Day 1. Women who are surgically sterile or those who are postmenopausal for at least 1 year are not considered to be of childbearing potential.

3.2 Exclusion criteria

Patients should not enter the study if any of the following exclusion criteria are fulfilled:

1. Involvement in the planning and/or conduct of the study (applies to both AstraZeneca staff and/or staff at the study site)
2. Cause or symptoms of pseudohyperkalemia, such as
 - 1) hemolyzed blood specimen due to excessive fist clenching to make veins prominent
 - 2) hemolyzed blood specimen due to difficult or traumatic venepuncture
 - 3) history of severe leukocytosis or thrombocytosis
3. Patients treated with lactulose, rifaxan (rifaximin), or other non-absorbed antibiotics for hyperammonemia within 7 days prior to first dose of ZS.

4. Patients treated with resins (such as sevelamer hydrochloride, sodium polystyrene sulfonate [SPS; e.g. Kayexalate®] or calcium polystyrene sulfonate [CPS]), calcium acetate, calcium carbonate, or lanthanum carbonate, within 7 days prior to the first dose of study drug. Washout of SPS and CPS for 7 days (or longer) prior to the first dose of ZS is allowed, if termination of CPS or SPS is judged to be clinically acceptable by the investigator. Documented informed consent has to be obtained prior to the washout.
5. Patients with a life expectancy of less than 12 months
6. Patients who are severely physically or mentally incapacitated and who, in the opinion of investigator, are unable to perform the patients' tasks associated with the protocol
7. Female patients who are pregnant, lactating, or planning to become pregnant
8. Patients who have an active or history of diabetic ketoacidosis
9. Presence of any condition which, in the opinion of the investigator, places the patient at undue risk or potentially jeopardizes the quality of the data to be generated
10. Known hypersensitivity or previous anaphylaxis to ZS or to components thereof
11. Treatment with a drug or device within the last 30 days that has not received regulatory approval at the time of study entry.
12. Patients with cardiac arrhythmias that require immediate treatment
13. Hemodialysis patients (including those who are on both PD and hemodialysis [HD])
14. Patients who have been on PD less than 6 months or more than 6 months with a history of hypokalemia within 6 months before Correction Phase Day 1
15. Documented Glomerular Filtration Rate (GFR) < 15 mL/min within 90 days prior to study entry (Non peritoneal dialysis (PD) patients only)
16. If patients joined ZS study in the past, the patients cannot join this study within the last 30 days of the last study drug administration day.

For procedures for withdrawal of incorrectly enrolled patients, see Section 3.4.

3.3 Patient enrolment

Investigator(s) should keep a record, the patient screening log, of patients who entered pre-study screening.

The Investigator(s) will:

1. Obtain signed informed consent from the potential patient or their guardian/legal representative before any study specific procedures are performed. Patient is considered enrolled in the study after she/he has signed the informed consent form (ICF).
2. Assign potential patient a unique enrolment number via Interactive Voice Response System (IVRS) / Interactive Web Response System (IWRS), beginning with 'E#'. .
3. Patients will remain associated with the same enrolment number throughout the entire study, and patients should NOT receive any new E-code if re-screened. If a patient signs the ICF but does not meet the inclusion/exclusion criteria the patient will be marked as a screen failure on the Screening and Enrolment Log provided by the Sponsor and will be entered in the Web Based Data Capture (WBDC) as a screen failure. Patients can be re-screened once. A new ICF does not need to be signed before re-screening if the original ICF was signed within 30 days and the ICF has not been revised.

If a patient withdraws from participation in the study, then his/her enrolment code cannot be reused.

3.4 Procedures for handling incorrectly enrolled

Patients who fail to meet the eligibility criteria should not, under any circumstances, be enrolled or receive study medication. There can be no exceptions to this rule. Patients who are enrolled, but subsequently found not to meet all the eligibility criteria must not start treatment, and must be withdrawn from the study.

Where a patient does not meet all the eligibility criteria but is incorrectly started on treatment, the Investigator should inform the AstraZeneca study physician immediately, and a discussion should occur between the AstraZeneca study physician and the Investigator regarding whether to continue or discontinue the patient from treatment. The AstraZeneca study physician must ensure all decisions are appropriately documented.

3.5 Methods for assigning treatment groups (Not Applicable)

3.6 Methods for ensuring blinding (Not Applicable)

3.7 Methods for unblinding (Not Applicable)

3.8 Restrictions

For concomitant medications which are restricted during the study, please see Section 7.7.

3.9 Discontinuation of investigational product

Patients may be discontinued from investigational product (IP) in the following situations:

- Patient decision. The patient is at any time free to discontinue treatment, without prejudice to further treatment
- Adverse Event
- Severe non-compliance with the Clinical Study Protocol
- Risk to patient as judged by investigator
- Pregnancy
- Require treatment with medications prohibited or contraindicated for use due to safety concerns with ZS
- Patient develops potassium values which meet the IP discontinuation criteria described in [Table 6](#) (confirmed by taking a second potassium measurement after a 10 ± 2 -minute interval, and both i-STAT values meet the study drug discontinuation rule). Patients discontinuing due to this criterion must immediately receive appropriate medical treatment to manage their hypo- or hyperkalemia.

Patient develops clinically significant cardiac condition (see below). The patient should immediately receive appropriate medical treatment and be discontinued from study drug.

- Serious cardiac arrhythmias (ventricular tachycardia or ventricular fibrillation, new atrial fibrillation or atrial flutter, new paroxysmal supraventricular tachycardia [other than sinus tachycardia], new 2nd or 3rd degree AV block or significant bradycardia [HR < 40 bpm])
- Acute heart failure
- Significant increase in PR interval (> 250 msec in the absence of pre-existing atrioventricular block) or widening of the QRS complex (>140 msec in the absence of pre-existing bundle branch block). If an ECG shows peaked T-wave, the serum potassium must be checked immediately and decide whether to continue the IP based on the criteria described in [Section 3.9](#).
- An absolute QTc >550msec, or an increase in QTc interval > 60msec from baseline to more than 500msec. All patients meeting the QTc>500ms criterion should immediately have potassium assessed by i-STAT and central lab, if not already done within 1 hour of the collection of the ECG

Patients who discontinue from study medication during the Correction Phase conduct Visit5 procedure soon after the discontinuation and conduct EOS Visit one week after last IP.

Patients who discontinue from study medication during the Maintenance Phase conduct Visit23 procedure soon after the discontinuation and conduct EOS Visit one week after last IP.

At the time of IP discontinuation, procedures will be performed in accordance with the required order whenever possible, see [Section 4.2.4](#) and [4.2.11](#).

3.9.1 Procedures for discontinuation of a subject from investigational product

At any time, patients are free to discontinue investigational product or withdraw from the study (i.e., investigational product and assessments – see Section 3.10), without prejudice to further treatment. A patient that decides to discontinue investigational product will always be asked about the reason(s) and the presence of any adverse events. If possible, they will be seen and assessed by an Investigator(s). Adverse events will be followed up; and all study drugs should be returned by the patient.

If a patient is withdrawn from study, see Section 3.10.

3.10 Criteria for withdrawal

The term withdrawal from the study refers to discontinuation from both study medication and study assessments.

Specific reasons for withdrawal from study are:

- Voluntary discontinuation by the patient who is at any time free to discontinue his/her participation in the study, without prejudice to further treatment (see Section 3.10.2)
- Severe non-compliance to protocol as judged by the Investigator and/or Sponsor
- Lost of patient to follow-up
- Death

Any patient who is withdrawn from the study medication prior to study completion will return to the clinic 7 (\pm 1) days after the last IP administration for an EOS visit. Dosing schedule cards and all study drugs should be returned by the patient.

The date and reason for patient withdrawal must be recorded on the appropriate electronic Case Report Form (eCRF). Every attempt should be made to contact any patient considered lost to follow-up.

It is understood by all concerned that an excessive rate of withdrawals can render the study un-interpretable; therefore, unnecessary withdrawal of patients should be avoided.

3.10.1 Screen failures

Screening failures are patients who do not fulfil the eligibility criteria for the study, and therefore must not be entered into the study, i.e. patients that are withdrawn prior to receiving open label treatment. These patients should have the reason for study withdrawal recorded as 'Eligibility criteria not fulfilled' (i.e., patient does not meet the required inclusion/exclusion criteria). This reason for study withdrawal is only valid for screen failures.

3.10.2 Withdrawal of the informed consent

Patients are free to withdraw from the study at any time (investigational product and assessments), without prejudice to further treatment.

A patient who withdraws consent will always be asked about the reason(s) and the presence of any adverse events. The Investigator will follow up AEs outside of the clinical study.

If a patient withdraws from participation in the study, then his/her enrolment code cannot be reused. Withdrawn patients will not be replaced.

3.11 Interruption of investigational product

Investigational product (IP) may be interrupted in situations such as an adverse event, laboratory abnormality other than potassium abnormality (only during Maintenance Phase) at the investigator's discretion.

During an interruption of IP, the patient will return to the site at least every 7 (\pm 2) days as an extra visit for a potassium measurement and recording of any adverse events and concomitant medications (Patient will arrive at the clinic in the morning after fasting for at least 8 hours prior to potassium sample collection.). In case it is unlikely to re-start IP, patient should be discontinued from the IP. On each extra visit, investigator and sponsor should discuss the study continuation. When the patient re-start IP, dose should be the same as the last dose before interruption. If the IP was interrupted due to an AE, the causality of the AE must be judged by investigator to be not related to IP upon resuming the IP.

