1.4 Study Design

The study is an open label, single arm study with flexible dose regimen focused on assessing long-term safety and tolerability of ZS in Japanese subjects with hyperkalemia.

Correction Phase: If the subject is normokalemic (i-STAT potassium between 3.5 and 5.0 mmol/L, inclusive) on the morning of Correction Phase Study Day 2 after 3 doses of ZS 10 g, they will enter the Maintenance Phase. If the subject is not normokalemic, they will receive an additional 24 hours of ZS 10 g TID treatment (6 total doses). If the subject's i-STAT potassium value is between 3.5 and 5.0 mmol/L, inclusive, on the morning of Correction Phase Study Day 3, the subject will enter the Maintenance Phase. If the subject is not normokalemic, they will receive an additional 24 hours of ZS 10 g TID treatment (9 total

doses). If the subject's i-STAT potassium value is between 3.5 and 5.0 mmol/L, inclusive, on the morning of Correction Phase Study Day 4, the subject will enter the Maintenance Phase. If the i-STAT potassium value is still < 3.5 mmol/L or ≥ 5.1 mmol/L on the morning of Correction Phase Study Day 4, after 72 hours of TID treatment, the subject will be withdrawn from the study and referred to their normal health care provider for standard of care treatment. Subjects withdrawn from the Correction Phase of the study will return to the clinic $7 (\pm 1)$ days after their last dose of ZS for an End of Study (EOS) visit.

[figure not shown]
Maintenance Phase: Patients will initially be dosed with ZS at a starting dose of 5g QD. Potassium (i-STAT and central laboratory) will be measured as indicated in the study schedule (Table 2). During the Maintenance Phase, the ZS dose may be increased up to 15 g QD or decreased down to 5g QOD (or 2.5 g QD) based on i-STAT potassium measurements as outlined in Section 7.2.

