2. STUDY OBJECTIVES

2.1 Primary objective

Primary Objective:	Outcome Measure:
Maintenance Phase To assess open-label, long-term (12 months) safety and tolerability for ZS in Japanese subjects with hyperkalemia (serum potassium ≥ 5.1 mmol/L).	Safety and tolerability as measured by adverse events reporting, vital signs, ECGs, physical examinations, and safety laboratory measurements.

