6.3.3 Variables

The following variables will be collect for each AE;

- AE (verbatim)
- The date when the AE started and stopped
- Maximum intensity
- Whether the AE is serious or not
- Investigator causality rating against the Investigational Product (yes or no)
- Action taken with regard to investigational product
- Outcome.

In addition, the following variables will be collected for SAEs:

- Date AE met criteria for serious AE
- Date Investigator became aware of serious AE
- AE is serious due to
- Date of hospitalization
- Date of discharge
- Probable cause of death
- Date of death
- Autopsy performed
- Causality assessment in relation to Study procedure(s)
- Causality assessment to other medication
- Description of AE.

Intensity rating scale:

- 1 mild (awareness of sign or symptom, but easily tolerated)
- 2 moderate (discomfort sufficient to cause interference with normal activities)
- 3 severe (incapacitating, with inability to perform normal activities)

It is important to distinguish between serious and severe AEs. Severity is a measure of intensity whereas seriousness is defined by the criteria in Section 6.2. An AE of severe

intensity need not necessarily be considered serious. For example, nausea that persists for several hours may be considered severe nausea, but not a SAE unless it meets the criteria shown in Section 6.2. On the other hand, a stroke that results in only a limited degree of disability may be considered a mild stroke but would be a SAE when it satisfies the criteria shown in Section 6.2.

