6.3.4 Causality collection

The Investigator will assess causal relationship between Investigational Product and each Adverse Event, and answer ‘yes’ or ‘no’ to the question ‘Do you consider that there is a reasonable possibility that the event may have been caused by the investigational product?’

For SAEs causal relationship will also be assessed for other medication and study procedures. Note that for SAEs that could be associated with any study procedure the causal relationship is implied as ‘yes’.

A guide to the interpretation of the causality question is found in [Appendix A](#) to the Clinical Study Protocol.

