8.5.2 Analysis of Safety data

Safety analyses will be performed separately for the correction phase and maintenance phase. Safety endpoints will include adverse events (including incidence of Oedema related events, defined as Fluid overload, Fluid retention, Generalised oedema, Hypervolaemia, Localised oedema, Oedema, Oedema peripheral and Peripheral swelling), vital signs, and other relevant clinical chemistry (specifically, the incidence of hypokalemia, hypomagnesemia, hypophosphatemia, and hypocalcemia), hematology, and urinalysis parameters. Kidney function will be evaluated by assessments of creatinine, eGFR, urine protein-to-creatinine ratio (UPCR) and urine albumin-to-creatinine ratio (UACR) over time. Liver function will be evaluated by assessing bilirubin, AST and ALT.

Treatment emergent AEs (TEAE) will be mainly analyzed. Adverse events will be classified by the Medical Dictionary for Regulatory Activities (MedDRA) to be consistent with other ZS studies. Safety data will be collected and analyzed while on study phases and reported until treatment-emergent adverse events are resolved. Unresolved adverse event outcomes at the end of treatment will be followed for an additional 7 days or until resolution, whichever occurs earlier. The type, incidence, timing (onset, duration), relationship, and severity of adverse events will be reported for treatment-emergent and serious adverse events. Reasons for withdrawal due to adverse events will also be reported. Narratives will be written for every adverse event classified as serious or associated with death.

Vital signs, ECGs and laboratory measurements will also be summarized descriptively.

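### Section 3.11 makes resuming ZS after an AE depend on the same yes/no causality rating that the safety analysis reports, which could lower the related-AE incidence by an unknown amount

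*Protocol*

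**What the plan says.** Section 3.11 of the protocol, added in version 5.0, allows ZS to be interrupted at the investigator's discretion, for example for an adverse event. On restart after such an event it requires that "the causality of the AE must be judged by investigator to be not related to IP upon resuming the IP". It adds: "On each extra visit, investigator and sponsor should discuss the study continuation". A patient who is unlikely to restart is to be discontinued from ZS.

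Section 6.3.3 lists, for every AE, one investigator yes/no rating of causality against ZS. Section 6.3.4 gives the question behind it: "Do you consider that there is a reasonable possibility that the event may have been caused by the investigational product". Neither section mentions restart, and neither says when the rating becomes fixed.

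The primary outcome measure in section 2.1 is "Safety and tolerability as measured by adverse events reporting, vital signs, ECGs, physical examinations, and safety laboratory measurements". Section 8.5.2 then states: "The type, incidence, timing (onset, duration), relationship, and severity of adverse events will be reported for treatment-emergent and serious adverse events". On design, section 1.4 says: "The study is an open label, single arm study with flexible dose regimen".

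**The concern.** A causality rating is informative only if it records what the rater thinks about cause. Under section 3.11 the answer also decides whether the patient can go back on ZS. An investigator who believes that continuing is in the patient's interest then has a reason, unrelated to causality, to answer 'no'.

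The study has no comparator, so no control-arm rate exists against which a shifted related-AE incidence could be recognised. The protocol also names no independent review of causality. If the restart decision colours the ratings, the table of related events would understate attribution for events that led to an interruption and were followed by a restart.

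**Working it through.** **Step 1: follow the judgement through the text.**

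- Section 3.11: 'not related' is the condition for resuming after an AE interruption.
- Sections 6.3.3 and 6.3.4: the only investigator causality variable against ZS is one yes/no rating per AE.
- Section 8.5.2: that attribute is reported for treatment-emergent and serious events.

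The protocol provides no second field for the restart judgement, so the two uses share one rating.

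**Step 2: direction of the incentive.** A 'not related' rating permits restart. A 'related' rating leaves no way back, and section 3.11 sends such a patient to discontinuation. Section 3.10 asks sites not to withdraw patients needlessly, section 3.10.2 says that withdrawn patients are not replaced, and section 8.2 needs at least 100 subjects with one year of treatment. Nothing in the protocol pushes towards 'related'. Appendix A counts improvement after stopping the drug as a point in favour of causality. An event that clears during the interruption can therefore gain evidence for 'related' just when 'not related' is needed for restart.

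**Step 3: the plan's own figure.** Section 8.2 gives about 150 subjects for at least 100 treated one year at about 35% dropout. Check: 100 / (1 − 0.35) = 153.8, so 154; the stated 150 differs by 4, or 4/150 = 2.7%. Forward: 150 × 0.65 = 97.5. The figure reproduces to within rounding. It is not in dispute and serves below only as the denominator.

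**Step 4: possible size.** The protocol gives no rate for AEs, interruptions or relatedness, so every rate here is an assumption:

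- *i* = share of subjects with an AE interruption considered for restart, 5% to 20%
- *r* = share of those AEs that would be rated related if rated freely, 20% to 50%
- *f* = share of those rated 'not related' in order to permit restart, 25% to 100%

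Subjects no longer counted for that event = 150 × *i* × *r* × *f*. Percentage points = 100 × *i* × *r* × *f*, which does not depend on the denominator.

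| Case | *i* | *r* | *f* | Subjects | Points |
|---|---|---|---|---|---|
| No influence | any | any | 0 | 0 | 0 |
| Low | 0.05 | 0.20 | 0.25 | 0.375 | 0.25 |
| Middle | 0.10 | 0.50 | 0.50 | 3.75 | 2.5 |
| Worst | 0.20 | 0.50 | 1.00 | 15 | 10 |

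Each row also assumes that the affected subject has no other AE rated related. A subject who has one stays in the related-AE incidence whatever happens to this event.

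**The case against.** The strongest reply is that section 3.11 sets a condition for restart and does not tell anyone to change a rating. An investigator who answers the section 6.3.4 question honestly keeps 'related', the patient does not restart, and the event is still counted. The clause also has an evident safety purpose, since Appendix A says that the sponsor would not normally support re-challenge. This stands. A reader might infer that the rule by itself converts every event followed by a restart into 'not related' and so removes related events. The text supports only that restarts follow events judged not related. Events disappear from the related count only if the wish to restart changes the answer.

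Safeguards exist. Section 6.3.3 collects the action taken with ZS for each AE, so events leading to interruption can be found whatever their rating. Section 9.4 provides an audit trail, so an overwritten 'yes' can be recovered. Section 8.5.2 requires narratives for serious events. These help, but none protects a first rating already made with restart in mind.

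Two further inferences would go too far. One is that the primary endpoint is biased: section 2.1 names AE reporting as a whole, relationship is one descriptive attribute of it, and section 8.5.1 plans no formal testing. The other is that the affected events are especially serious: interruption is discretionary, with no severity threshold.

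Finally, tabulation rules may well sit in the statistical analysis plan, which is not at hand. That is fair for the tables. It does not cover how the rating is produced at site, which the protocol itself governs and no later analysis plan can undo.

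**Conclusion.** The point holds as a conditional one. Section 3.11 lets a treatment decision and a reported safety attribute rest on the same judgement, with an incentive in one direction only, in a study without a comparator. The reported related-AE incidence could therefore be too low for events followed by a restart. The protocol does not show that it will be.

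The size cannot be determined. It is zero if ratings are made without regard to restart. Under the assumed rates it runs from about 0.25 to 10 percentage points, with a middle case of 2.5 points (3.75 of 150 subjects). The 10 points need a 20% interruption share, half of those events truly thought related, and every one of them rated to allow restart.

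The reach is limited. All-cause AE and SAE counts do not change. The rule came with version 5.0, dated 13 September 2018, in a study expected to run from Q2 2017 to Q3 2019, so it covers only part of follow-up. This is a cheap improvement to make; it does not invalidate the safety analysis.

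**What to change.** Leave the restart rule in section 3.11 as it is; whether dosing may resume is a clinical matter and is not judged here. Change only how the data are recorded and reported:

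- In sections 3.11 and 6.3.4, state that the causality rating is entered before the restart decision and separately from it, and that any later change is kept with its date and reason.
- Give the restart judgement its own eCRF field.
- In section 8.5.2, tabulate related AEs as ever rated related, list ratings that changed around a restart, and show all AEs leading to interruption regardless of causality. The action-taken field already collected supports the last item.
- For ratings entered before the change, take the first entry from the audit trail.

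The cost is about one eCRF field and a few sentences of text, together with a related-AE count that may look slightly less favourable.
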